5 DEMOGRAPHICS AND BASELINE CHARACTERISTICS

5.1 Demographics

Demographic data will be summarized using descriptive summary statistics for the Safety Analysis Set. The demographic characteristics include age, sex, race, ethnicity, body height (in cm), body weight (in kg) and body mass index (BMI; in kg/m²).

A by-subject listing will be provided for demographic data.

5.2 Other Baseline Disease Characteristics

Other baseline characteristics include baseline ECOG PS and B7-H4 expression level by IHC. Summary of ECOG PS by treatment group for the Safety Analysis Set will be provided as part of the disease-specific baseline characteristics. A by-subject listing will be provided for B7-H4 expression level by IHC.

5.3 Medical History

Medical history will be collected at screening for disease-specific and general conditions (ie, conditions not specific to the disease being studied).

A summary of disease-specific medical history will be provided for the Safety Analysis Set as part of the disease-specific baseline characteristics. Time since initial diagnosis of cancer (months) and time since diagnosis of unresectable disease (months) will be calculated by (date of first dose – date of diagnosis) / 30.4375. They will be summarized using summary statistics for a continuous variable. Disease stage at diagnosis and at screening will be summarized using summary statistics for a categorical variable.

In deriving the time since diagnosis, all partial dates of diagnosis and last regimen will be identified, and the partial dates will be imputed as follows:

- If day and month are missing but year is available, then the imputed day and month will be 01 Jan.
- If day is missing but the month and year are available, then the imputed day will be the first day of the month.
- Partial date will not be imputed if the year is missing.

General medical history data will be listed only. By-subject listings will be provided for disease-specific medical history and general medical history.

5.4 Prior and Concomitant Medications

Prior and concomitant medications will be coded using the World Health Organization Drug Dictionary –WHODD and classified according to ATC codes levels 2 (therapeutic sublevel) and 4 (chemical sublevel).

All medications with an end date prior to the first dose of any study drug will be considered as prior medication regardless of the stop date. If a partial start date is entered the medication will be considered prior unless the month and year (if day is missing) or year (if day and month are missing) of the start date are after the first dosing date. Medications with a completely missing start date will be considered as prior medication, unless otherwise specified.

Concomitant medications are defined as medications taken while a subject took study drug. If a partial stop date is entered, any medication with the month and year (if day is missing) or year (if day and month are missing) prior to the date of first study drug administration will not be considered as concomitant medication. If a partial start date is entered, any medication with the month and year (if day is missing) or year (if day and month are missing) after the study drug stop date will not be considered as concomitant medication. Medications with completely missing start and stop dates will be considered as concomitant medication, unless otherwise specified.

All prior and concomitant medications (other than per-protocol study drugs) will be provided in a by-subject listing.

5.5 Prior Anticancer Therapy

Number of prior regimens, time since the completion of last regimen will be summarized by treatment group using descriptive statistics. The best response to the last regimen will be summarized using summary statistics for a categorical variable. The summaries will be based on the Safety Analysis Set as part of the disease-specific baseline characteristics. A partial completion date will be imputed using the algorithm defined in Section 5.3. The prior anticancer therapy will be listed by subject.

6 EFFICACY ANALYSES

Efficacy summaries will be presented by treatment group based on the Efficacy-Evaluable Analysis Set.

6.1 Objective Response Rate

ORR is defined as the proportion of subjects who achieve best overall response (BOR) of either complete response (CR) or partial response (PR) based on investigator assessment tumor lesions per RECIST v1.1. The BOR is the best response documented from first dose until the end of study, first disease progression, death, or start of new anti-cancer therapy, whichever is earlier. Subjects, who do not have sufficient baseline or on-study tumor status information to be adequately assessed for response status (i.e., those with BOR of not evaluable [NE]), or received anticancer therapy other than the study treatment, will be considered as non-responders and will be included in the denominators in calculations of response rates.

When the date of initiation of new anticancer therapy other than the study treatment is incomplete or missing, the following algorithm will be followed:

- If the day is missing but the month and year are available, then the imputed day will be the last day of the month.
- If day and month are missing but year is available, then the imputed day and month will be the last day of the month for the last adequate disease assessment if they have the same year.

The analysis of ORR will be performed based on the Efficacy-Evaluable Analysis Set. ORR with corresponding 2-sided 95% CI based on Clopper-Pearson method along with each category of BOR will be summarized by treatment group. Patients who don't have any postbaseline adequate tumor assessments will be counted as non-responders.

By-subject listings will be provided for target lesion, nontarget lesion, new lesion, and investigator-assessed timepoint response. A by-subject listing of new anticancer therapy will also be provided.

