9.4.2 Efficacy Analyses

The ORR will be summarized with frequencies and percentages with 90% CI by each dose/cohort. The duration of response (DOR) for complete response (CR) and partial response (PR) patients and PFS for all treated patients will be summarized with descriptive statistics (N, arithmetic mean, SD, median, minimum, and maximum). The ORR, DOR, and PFS will

be determined using RECIST v1.1. Kaplan-Meier methodology will be used to estimate median DOR and PFS and corresponding 95% CI.

ORR, DOR, and PFS are defined below.

ORR: defined as the total number of patients with confirmed responses of either CR or PR per RECIST v1.1 divided by the total number of patients who are evaluable for a response.

DOR: defined as the time from onset of response (CR or PR) that is subsequently confirmed to the first observation of progressive disease or death due to any cause. Patients who are alive and progression-free at the time of data analysis will be censored at the time of their last assessment for tumor response.

PFS: defined as the time from the patient's first dose to the first observation of progressive disease or death due to any cause. Patients who are alive and progression-free at the time of data analysis will be censored at the time of their last assessment for tumor response.

More details of censoring rule for DOR and PFS will be outlined in SAP.

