EXPLORATORY - EFFICACY	

FPA150 Monotherapy
 
 • To evaluate the clinical benefit of FPA150 as monotherapy 	
FPA150 Monotherapy
 
 • ORR defined as the total number of patients with confirmed responses of either CR or PR per Response Evaluation Criteria in Solid Tumors (RECIST) v1.1 divided by the total number of patients who are evaluable for a response • Duration of response (DOR), defined as the time from onset of response (CR or PR) that is subsequently confirmed to the first observation of progressive disease or death due to any cause • Progression free-survival (PFS), defined as the time from the patient's first dose to the first observation of progressive disease or death

FPA150 in Combination with Pembrolizumab
 
 • To evaluate the clinical benefit of FPA150 in combination with pembrolizumab in patients with B7-H4+ ovarian cancer 	
FPA150 in Combination with Pembrolizumab
 
 • ORR, defined as the total number of patients with confirmed responses of either CR or PR per RECIST v1.1 divided by the total number of patients who are evaluable for a response • DOR, defined as the time from onset of response (CR or PR) that is subsequently confirmed to the first observation of progressive disease or death due to any cause • PFS, defined as the time from a patient's first dose to the first observation of progressive disease or death due to any cause.
EXPLORATORY - Pharmacokinetics	

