1.2.2 Phase 1b Objectives and Endpoints

[figure not shown]

The objectives and endpoints for Phase 1b of the study are summarized in Table 6.

Table 6: Objectives and Endpoints: Phase 1b

OBJECTIVES	ENDPOINTS
PRIMARY - SAFETY	
FPA150 Monotherapy 
 To evaluate the safety and tolerability of FPA150 as monotherapy in patients with B7-H4+ advanced solid tumors treated at the MTD and/or RD 	FPA150 Monotherapy 
 The incidence of AEs, clinical laboratory abnormalities, and ECG abnormalities
FPA150 Combined with Pembrolizumab 
 To evaluate the safety and tolerability of FPA150 in combination with pembrolizumab in selected 	FPA150 Combined with Pembrolizumab 
 The incidence of AEs, clinical laboratory abnormalities, and ECG abnormalities in patients

OBJECTIVES	ENDPOINTS
patients with B7-H4+ ovarian cancer treated at the MTD and/or RD	treated with FPA150 in combination with pembrolizumab
SECONDARY - EFFICACY	

FPA150 Monotherapy
 
 • To evaluate the clinical benefit of FPA150 as monotherapy in patients with B7-H4+ advanced solid tumors treated at the MTD and/or RD 	
FPA150 Monotherapy
 
 • ORR, defined as the total number of patients with confirmed responses of either CR or PR per RECIST v1.1 divided by the total number of patients who are evaluable for a response • DOR, defined as the time from onset of response (CR or PR) that is subsequently confirmed to the first observation of progressive disease or death due to any cause • PFS, defined as the time from the patient's first dose to the first observation of progressive disease or death due to any cause)

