
FPA150 in Combination with Pembrolizumab
 
 • To evaluate the clinical benefit of FPA150 in combination with pembrolizumab in patients with B7-H4 + ovarian cancer treated at the MTD and/or RD 	
FPA150 in Combination with Pembrolizumab
 
 • ORR, defined as the total number of patients with confirmed responses of either CR or PR per Response Evaluation Criteria in Solid Tumors (RECIST) v1.1 divided by the total number of patients who are evaluable for a response to FPA 150 combined with pembrolizumab • DOR, defined as the time from onset of response (CR or PR) that is subsequently confirmed to the first observation of progressive disease or death due to any cause to FPA150 combined with pembrolizumab • PFS, defined as the time from the patient's first dose to the first observation of progressive disease or death due to any cause to FPA150 combined with pembrolizumab
SECONDARY - PHARMACOKINETICS	

FPA150 Monotherapy
 
 • To characterize the PK profile of FPA150 as monotherapy in patients with B7-H4+ advanced solid tumors treated at the MTD and/or RD 	
FPA150 Monotherapy
 
 • AUC • C_{max} • C_{trough} • CL • t_{1/2} • V_{ss} • Other parameters, such as accumulation ratio, attainment of steady state, will also be calculated if the data are available

OBJECTIVES	ENDPOINTS
SECONDARY - IMMUNOGENICITY	

FPA150 Monotherapy
 
 To characterize the immunogenicity of FPA150 as monotherapy in patients with B7-H4+ advanced solid tumors treated at the MTD and/or RD 	
FPA150 Monotherapy
 
 Immune response (ADAs) to FPA150
EXPLORATORY - PHARMACOKINETICS	

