6.3 Changes from Protocol-Specified Efficacy Analysis

Analysis and summary will not be provided for time to duration of response and progression-free

survival due to limitation of the data.

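### SAP 6.1 derives ORR from best overall response with no confirmation step, although the protocol and the SAP's own endpoint tables define ORR on confirmed responses and SAP 6.3 declares no change

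*SAP*

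**What the plan says.** Protocol 9.4.2 gives ORR as "defined as the total number of patients with confirmed responses of either CR or PR per RECIST v1.1 divided by the total number" of evaluable patients. The SAP repeats the confirmed definition in its endpoint tables: Table 5 for Phase 1a ("ORR defined as the total number of patients with confirmed responses of either CR or PR per Response Evaluation Criteria in Solid Tumors"), and Table 6 for Phase 1b monotherapy ("ORR, defined as the total number of patients with confirmed responses of either CR or PR per RECIST v1.1") and for the combination ("ORR, defined as the total number of patients with confirmed responses of either CR or PR per Response Evaluation Criteria in Solid Tumors").

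SAP 6.1 gives the derivation: "ORR is defined as the proportion of subjects who achieve best overall response (BOR) of either complete response (CR) or partial response (PR"), by investigator assessment under RECIST v1.1. Best overall response (BOR) is then the "best response documented from first dose until the end of study, first disease progression, death, or start of new anti-cancer therapy", whichever comes first. Confirmation is not mentioned. The next sentence lists who counts as a non-responder, including subjects who cannot be assessed "or received anticancer therapy other than the study treatment, will be considered as non-responders". The estimate is reported with a two-sided 95% Clopper-Pearson interval.

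SAP 6.3, the section for changes from the protocol's efficacy analysis, contains one item: "Analysis and summary will not be provided for time to duration of response and progression-free" survival. It does not mention ORR.

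**The concern.** The SAP holds two definitions of the same endpoint. The tables say confirmed; the derivation does not. A programmer working from 6.1 alone would count a CR or PR seen once and not seen again, and the resulting table would carry the name of an endpoint that the protocol defines more strictly.

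This matters more here than it usually would. SAP 6.3 drops duration of response and PFS, and SAP section 6 plans no overall survival analysis, so ORR is the only efficacy endpoint still summarized. With duration of response gone, confirmation is the one remaining feature of the efficacy table that says anything about whether a response lasted. The ORR table as specified would not show which responses were confirmed.

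A smaller wording problem sits in the same paragraph. The BOR window closes when new anticancer therapy starts, so an earlier response is kept. The non-responder clause on other anticancer therapy has no timing limit.

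**Working it through.** **1. Definitions side by side**

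| Place | What is counted |
|---|---|
| Protocol 9.4.2 | confirmed CR or PR |
| SAP Table 5 (Phase 1a) | confirmed CR or PR |
| SAP Table 6 (Phase 1b, monotherapy and combination) | confirmed CR or PR |
| SAP 6.1 (derivation) | BOR of CR or PR; confirmation not mentioned |
| SAP 6.3 (declared changes) | nothing on ORR |

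**2. Direction.** With the same window and denominator, confirmed responders are a subset of subjects with any documented CR or PR. If *u* subjects have a response that is never confirmed, then

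ORR (6.1 read literally) − ORR (confirmed) = *u*/*n* ≥ 0, and it equals 0 when *u* = 0.

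**3. Interval method.** Clopper-Pearson limits for *x* responders in *n* at level 1−α are: lower = the α/2 quantile of Beta(*x*, *n*−*x*+1); upper = the 1−α/2 quantile of Beta(*x*+1, *n*−*x*). As a check, SAP Table 7 gives (11%, 42%) for 6/25 at 90%. The formula gives 11.0% and 42.0%, so the plan's figure is reproduced. Table 7 is a design table at 90%. The ORR table planned in 6.1 uses 95%, so 95% is used below.

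**4. Illustration.** Inputs: *n* = 25, the planned evaluable number per Phase 1b cohort (SAP 1.3); 6 responders under 6.1, which is the 24% row of Table 7; *u* is assumed, because the documents give no confirmation rate.

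| Unconfirmed, *u* | Confirmed ORR | 95% Clopper-Pearson | Shift |
|---|---|---|---|
| 0 | 6/25 = 24% | 9.4% to 45.1% | 0 |
| 1 | 5/25 = 20% | 6.8% to 40.7% | 1/25 = 4 points |
| 2 | 4/25 = 16% | 4.5% to 36.1% | 2/25 = 8 points |

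**5. Can confirmation be assessed with the planned scans?** Protocol Appendix 1, footnote k, sets scans every 6 weeks ± 1 week for the first 6 months. The shortest gap between consecutive scheduled scans is (12 − 1) − (6 + 1) = 4 weeks. A minimum interval of 4 weeks therefore fits the schedule without extra imaging.

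**6. New-therapy clause.** Take a subject with a PR on study who later starts another anticancer therapy. Under the window sentence the PR stands. Under the clause read literally the subject is a non-responder. SAP 6.1 also gives rules for imputing incomplete start dates of new therapy. If other therapy at any time meant non-response, those dates would have no effect on ORR, so the imputation rules point to a date-bound rule.

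**The case against.** The best answer is that the SAP does say confirmed, in three endpoint definitions, and that 6.1 only elaborates them by naming the assessor, the window and the denominator. On that view one word is missing, and the silence of 6.3 fits because no change was meant. This may well be the intention. It does not remove the fault, because 6.1 is the operative text and gives neither the requirement nor an interval. The reference in 6.1 to RECIST v1.1 does not settle it either: the protocol and the SAP tables cite RECIST v1.1 and still add confirmed, so the sponsor did not treat the citation as enough.

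It is also fair that the primary endpoints are safety (Protocol 4.5), that all analyses are descriptive (Protocol 9.3), that no formal testing is planned (SAP 3.4), and that the by-subject listings of timepoint response in 6.1 would let a reader recover the difference. These points limit the severity and stand.

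Two stronger readings are tempting, and the documents support neither:

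- A reader might infer that one unconfirmed response decides whether the interval excludes the 10% rate named in SAP 1.3. In the 95% interval that 6.1 plans, 6/25 already has a lower limit of 9.4%, so 10% is not excluded even before a response is removed. The 10% figure is in any case a precision benchmark for sample size, with no decision attached.
- A reader might infer that the therapy clause biases ORR downward. The window sentence and the start-date imputation both point to a rule bound by date. What remains is unclear wording, with no bias shown.

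**Conclusion.** The point holds as an inconsistency between the SAP's derivation and the endpoint definition in the protocol and the SAP's own tables, with no declared change. It should be fixed. Confidence is high that the confirmation step is missing from 6.1. It is not established that the reported ORR will differ: that depends on how the derivation is programmed and on how many responses fail to confirm.

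Missing confirmation can only raise ORR. The size is 4 points per unconfirmed response at *n* = 25 and zero if all confirm. These figures rest on the planned evaluable number and on assumed counts of unconfirmed responses. A reader might also infer a deliberate switch to unconfirmed ORR, but the confirmed definitions kept in Tables 5 and 6 speak against that.

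**What to change.** In SAP 6.1, define ORR as the proportion of subjects with a confirmed BOR of CR or PR per RECIST v1.1. State the minimum confirmation interval, which is for the sponsor to set; at least 4 weeks is an example that fits the 6-week ± 1 week schedule. State also that both assessments must fall within the BOR window, that is, before first progression and before new anticancer therapy.

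If unconfirmed ORR is what the sponsor wants, declare it in SAP 6.3 and label the table accordingly.

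Align the therapy clause with the window, for example: *or started other anticancer therapy before a confirmed response was documented*.

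The cost is SAP wording and one derivation. No new data are needed, because 6.1 already plans listings of investigator timepoint response and of new anticancer therapy. The downside is that a responder without a qualifying confirmatory scan will count as a non-responder.

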8.6 Efficacy Assessments

8.6.1 Tumor Assessment

The first on-study imaging assessment should be performed within 28 days from C1D1. Subsequent tumor assessments will be performed in accordance with the Schedule of Assessments (Appendix 1) and should consist of clinical examination and appropriate imaging techniques (preferably computed tomography (CT) scans with appropriate slice thickness per RECIST v1.1, magnetic resonance imaging (MRI) acceptable). The same methods used to detect lesions at baseline are to be used to follow the same lesions throughout the clinical study.

Tumor response assessment will be performed every 6 weeks for 6 months and then every 12 weeks by the Investigator per the Schedule of Assessments (Appendix 1) using RECIST v1.1 guidelines (Appendix 4) (Eisenhauer 2009).

If patient terminates prior to scheduled CT/MRI scans, patient should have scans done at the EOT visits (does not need to be repeated if performed within 8 weeks prior to the EOT visits, or if tumor progression was previously determined). After discontinuation of study treatment for reasons other than progressive disease, or withdrawal of consent, or initiation of additional anti-cancer therapy, tumor assessments will continue approximately every 12 weeks until disease progression, withdrawal of consent or start of new anti-cancer therapy.

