8.14.1 Long-Term Follow-Up

Long-term follow-up should be done in accordance with the Schedule of Assessments ([Appendix 1](#)). Patients enrolled in Phase 1b will be required to enter into long-term follow-up after they have permanently discontinued study drug (refer to [Section 7](#)) until death, withdrawal of consent or study termination. During long-term follow-up, patients should be contacted every 12 (± 2) weeks for survival status. Patients should have tumor scans every 12 (± 2) weeks, if tumor progression was not previously determined and/or use of alternative anti-cancer therapy has not been initiated. Any new anti-cancer therapy should be documented.

9 Statistical Considerations

Before database lock, a separate statistical analysis plan (SAP) will be finalized, providing detailed methods for the analyses outlined below.

Any deviations from the planned analyses will be described and justified in the final integrated study report.

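### SAP 6.1 gives two conflicting rules for new anticancer therapy, and its date imputation favours response if the best-overall-response window governs

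*SAP*

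**What the plan says.** SAP 6.1 ends the BOR window at the earliest of several events: end of study, or "first disease progression, death, or start of new anti-cancer therapy, whichever is earlier". The next sentence, which also covers subjects whose response cannot be evaluated, says of those who took other therapy: "received anticancer therapy other than the study treatment, will be considered as non-responders and will be included in the denominators". It does not say when that therapy must have begun.

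The same section then completes partial start dates of new therapy:
- Day missing: "If the day is missing but the month and year are available, then the imputed day will be the last day of the month".
- Day and month missing: "the imputed day and month will be the last day of the month for the last adequate disease assessment if they have the same year".
- Fully missing date, or a known year that differs from the year of the last assessment: no rule, although the algorithm is introduced for both incomplete and missing dates.

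Protocol 8.6.1 limits scans after study drug stops: "tumor assessments will continue approximately every 12 weeks until disease progression, withdrawal of consent or start of new anti-cancer therapy". Protocol 8.14.1 allows long-term follow-up scans "if tumor progression was not previously determined and/or use of alternative anti-cancer therapy has not been initiated". For end of treatment (EOT), however, Protocol 8.6.1 says: "If patient terminates prior to scheduled CT/MRI scans, patient should have scans done at the EOT visits". That scan is waived after earlier progression or a recent scan (within 8 weeks in 8.6.1, 6 weeks in Appendix 1 footnote k). Neither place waives it because new therapy has begun.

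Protocol 9.4.2 and SAP Tables 5 and 6 define ORR on confirmed responses. SAP 6.1 does not repeat that condition.

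**The concern.** A programmer following SAP 6.1 must choose between two rules that classify the same patient differently.

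Under the window rule, the start date of new therapy decides whether a late scan counts. Both imputation rules then resolve the uncertainty in favour of response. Elsewhere the SAP does the opposite: 7.1.3 counts an adverse event with missing relationship as related, and 7.1.5 counts an event with no dates as treatment-emergent.

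Under the non-responder sentence read literally, a patient with a confirmed response on study drug who progresses and then receives next-line therapy becomes a non-responder.

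SAP 6.3 drops duration of response and progression-free survival, so ORR with its BOR breakdown is the efficacy result that remains. It is investigator-read and has no control arm.

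**Working it through.** **1. The two rules applied to two patients.** Both are invented for illustration.

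- Patient A: PR confirmed on study drug, then progression, then next-line therapy with a complete date.
- Patient B: in the 12-weekly scan phase, PR first seen 20 January, last dose 1 March, new therapy recorded only as March (true start 8 March), EOT scan 29 March confirms the PR. From 20 January to 29 March is 11 + 28 + 29 = 68 days (non-leap year). That exceeds 8 weeks (56 days), so the EOT scan is not waived, and it is under 12 weeks (84 days), so the scheduled scan is not yet due.

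| Rule | Patient A | Patient B |
|---|---|---|
| Window, SAP imputation (31 March) | responder | confirmed responder; the 29 March scan is kept |
| Window, earliest plausible date (2 March) | responder | not confirmed; the 29 March scan is excluded |
| Non-responder sentence, literal | non-responder | non-responder, whatever the imputed date |

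**2. Length of the gap, day missing.** Gap = last day of month − true day. It runs from 0 to 30 days. The mean is 15.0 in a 31-day month, 14.5 in a 30-day month and 13.5 in a 28-day month. Over a 365-day year with uniform start days: (7 × 31 × 15.0 + 4 × 30 × 14.5 + 28 × 13.5) / 365 = 5,373 / 365 = 14.7 days.

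**3. Year only.** The imputed date is the month-end of the last adequate assessment, so it never precedes that assessment. When the years match, no adequate assessment is excluded. This assumes that an adequate assessment can be a post-switch scan; 6.1 does not define the term.

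**4. Size under the window rule, day missing.** The documents give no count of partial dates, so every input here is an assumption. Let *f* be the share of subjects who switch before progression with a day-missing date (2% to 10%), *g* the chance that a scan falls in the gap, and *q* the chance that such a scan newly shows response (10% to 30%). If scans continued every 6 weeks, *g* = 14.7/42 = 0.35; every 12 weeks, *g* = 14.7/84 = 0.175. The rise in ORR is *f* × *g* × *q*:
- low: 0.02 × 0.175 × 0.10 = 0.00035, or 0.04 points;
- high: 0.10 × 0.35 × 0.30 = 0.0105, or 1.1 points.

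This ignores confirmation and the limits on post-switch scans, both of which reduce the effect.

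**5. What one response does.** Exact (Clopper-Pearson) intervals for 25 evaluable patients reproduce SAP Table 7: 5/25 gives 8.2% to 37.5% (stated 8%, 38%) and 6/25 gives 11.0% to 42.0% (stated 11%, 42%). One response is 1/25 = 4 points.

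| Responses | 90% lower bound (planning, SAP 1.3) | 95% lower bound (analysis, SAP 6.1) |
|---|---|---|
| 5/25 | 8.2% | 6.8% |
| 6/25 | 11.0% | 9.4% |

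**6. Size under the literal sentence.** Each responder who later took other therapy costs 4 points. With 6/25 by the window rule, the loss ranges from 0 points (none did) to 6 × 4 = 24 points (all did). The documents give no number.

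**The case against.** A reader might infer that the imputation simply biases ORR upward. The documents do not support that without a condition. The non-responder sentence stands in the same paragraph and carries no date limit. Read literally, every subject with an imputed start date is already a non-responder, so the imputed day changes ORR by zero, and the sentence itself pushes ORR down.

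The path to an upward error is also narrow:
- BOR stops at first progression, so only a switch before progression matters, and the start date must be incomplete.
- Protocol 8.6.1 ends off-treatment scans at new therapy. Protocol 8.14.1 points the same way, although its and/or wording is loose. The EOT scan will often be waived when scans run every 6 weeks.
- The endpoint requires confirmation. A response first seen in a gap of at most 30 days could not normally be confirmed within it, because scheduled scans are 6 or 12 weeks apart. The realistic day-missing case is a response seen before the switch and confirmed after it.
- SAP 6.1 plans listings of timepoint response and new therapy, so an affected patient can be found.

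All of this stands and limits the size. It does not remove the conflict. The literal reading leaves the new-therapy clause of the window and the whole imputation algorithm with no function for ORR, and it produces the Patient A result. The imputed date could also still change the BOR categories tabulated beside ORR.

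**Conclusion.** SAP 6.1 conflicts with itself, and one of its two rules must change. If the window governs, the imputation resolves uncertainty in favour of response and can credit or confirm a response on a post-switch scan. The effect is probably small, 0.04 to 1.1 points on the assumptions shown, and needs a switch before progression, an incomplete date and a scan in the gap. If the non-responder sentence governs literally, the imputation has no effect on ORR, but genuine responders who later took next-line therapy are lost at 4 points each in a 25-patient cohort.

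Two stronger statements are not supported. One is that a single extra response lets the trial exclude 10%. That holds on the 90% planning interval (8.2% to 11.0%) but not on the 95% interval the SAP will report (6.8% to 9.4%), and SAP 3.4 plans no formal test. The other is that both rules use the latest possible date. The year-only rule stops at the month of the last adequate assessment and applies only when the years match.

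**What to change.** Amend SAP 6.1 as follows.

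1. State that the BOR window governs. Apply the non-responder rule for other anticancer therapy only to subjects with no qualifying (confirmed) response before that therapy starts.
2. Replace the imputation with the earliest plausible start date:
   - day missing: the later of the first of the known month and the day after the last study dose;
   - day and month missing: the later of 1 January of the known year and the day after the last study dose;
   - date fully missing but therapy recorded: the day after the last study dose.

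   The bound is reasonable because Protocol 6.10 bars other anticancer therapy during treatment. It also covers the two cases for which 6.1 has no rule. If the bound falls after the recorded month or year, query the date before imputing.
3. If any subject's BOR changes, show ORR under the current imputation as a sensitivity line. The earliest date can exclude a scan that truly preceded the switch, so readers should see both.

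The cost is a few lines of SAP text and derivation code, with no new data. With the confirmation requirement held fixed, ORR can only stay the same or fall relative to the window with the current imputation, and can only stay the same or rise relative to the literal non-responder sentence.
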